### PROBLEM STATEMENT

Depression, sleep concerns, addiction, and anxiety are leading and growing causes of disability, productivity loss, and premature mortality globally. The number of behavioral health clinicians available to provide face-to-face, traditional care is woefully inadequate to meet the growing need. Further, a substantial proportion of patients who receive traditional care do not get better. With inadequate evidence to meaningfully guide treatment decisions and few available objective measures of mental health symptoms, choice of treatment is often based on clinician preference and simple heuristics.

More than any other advance that has emerged in the past four decades, mobile technology has the potential to address the dual problems of limited clinical capacity and inadequate and untimely data. Mobile technology holds the potential to both track and intervene on mental health symptoms in powerful ways that had not previously been possible. However, little is known about how to derive the greatest value from this technology by targeting patients most likely to benefit and by providing clinicians with the most useful information gleaned from the intensive data collection processes in order to inform treatment decisions. Additionally, investigators continue to analyze genetic information as a predictor for mental health symptoms and outcomes. Genetic analysis, especially when coinciding with data gathered from mobile technology, may have the capacity to even further inform mental health treatment decisions and allow for comprehensive precision treatment.

### OBJECTIVES

As part of the Precision Health initiative at the University of Michigan, this project is focused on the effects of wearable and mobile technology to both reduce mental health symptoms and predict response to clinic-based treatments.

The overall goal of this project is to reduce the burden of mental health conditions by two means:

- 1) Increasing capacity in the mental health care system through expanding use of mobile technology-delivered interventions.
- 2) Accelerating recovery by matching patients to the pharmacological, psychological, and mobile-based treatments from which they will likely derive the greatest benefit.

To do so, we will complete the following **specific aims**:

**Aim 1:** To assess the independent and combined effectiveness of two classes of mobile technology interventions among patients while on the waitlist for traditional care:

- (a) App-based cognitive behavioral and mindfulness interventions
- (b) Enhanced objective, mobile data feedback on mood, sleep, heart rate, and activity levels

**Aim 2:** To use machine learning to identify key predictors of treatment response from mobile technology,

genomic, and environmental data collected from patients receiving:

- (a) Mobile technology interventions while on a waitlist for outpatient mental health care
- (b) Traditional face-to-face psychotherapy, medication, or neuromodulation treatment

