## **RESEARCH DESIGN AND METHODS**

This study will have **two phases**, each with different study designs:

**Phase 1** will cover the period while individuals are waiting for care. The design of this phase is a randomized clinical trial, wherein participants are randomly assigned to one of three study conditions that vary by the type of Mobile Health (mHealth) intervention they can receive.

**Phase 2** begins when a participant has a first appointment for outpatient mental health care, and uses a cohort study design for measuring outcomes associated with clinic-based treatments.

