### *App-Based Interventions*

Participants randomized to the groups receiving the apps will be asked to install an mHealth app onto their smartphone. The two apps that will be used are Headspace, an app designed to train the user in mindfulness practices, and Silvercloud, an app designed to deliver cognitive behavioral therapy. These apps were selected because of evidence of efficacy and applicability across a wide range of mental health symptoms. Participants receiving apps will be computer-assigned to receive one of the two options. Participants who were recruited with <2 weeks prior to their scheduled appointment (and thus not included in the initial randomization) will receive access to one of the two apps at the time of their intake appointment, also based on computer random assignment.

App notifications will encourage participants to use the apps regularly. If user data indicates that a participant is not using the apps, study staff will contact the participant via app notification, phone call, email, letter, or text message. SilverCloud allows for integration of a health coach as a supportive role for increasing engagement, largely through asynchronous messaging. Study staff will be trained in the role of the health coach and will engage with participants through the app to promote app use, personalization, and overall engagement. For both apps, study staff will provide ongoing technical assistance and address any participant barriers to app use.

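### Aim 2 looks for predictors of response among treated patients, which mixes prognosis with treatment effect; matching patients to treatments needs pre-specified predictor-by-assignment interactions

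*Combined protocol and SAP*

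**What the plan says.** Under OBJECTIVES, overall goal 2 is to speed recovery by "matching patients to the pharmacological, psychological, and mobile-based treatments from which they will likely derive the greatest benefit". Aim 2 begins "To use machine learning to identify key predictors of treatment response from mobile technology" and adds genomic and environmental data. It covers patients receiving (a) "Mobile technology interventions while on a waitlist for outpatient mental health care" and (b) "Traditional face-to-face psychotherapy, medication, or neuromodulation treatment". Response is not defined and no comparator is named.

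The ANALYSIS PLAN lists summaries, change scores, chi-square tests, t-tests, and regressions of each variant or haplotype on baseline PHQ and on PHQ change. It names no machine-learning model and no interaction with arm or app.

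The design assigns treatment twice. The Phase 1 section randomises participants to EF+SF, App+SF or App+EF+SF. Within the app arms, the App-Based Interventions section says: "Participants receiving apps will be computer-assigned to receive one of the two options". These are Headspace (mindfulness) and SilverCloud (cognitive behavioural therapy). Only one is described with a coach: "SilverCloud allows for integration of a health coach as a supportive role for increasing engagement".

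Clinic treatment is not randomised. Under RESEARCH DESIGN AND METHODS, Phase 2 "uses a cohort study design for measuring outcomes associated with clinic-based treatments". Of care in general, the PROBLEM STATEMENT says that "choice of treatment is often based on clinician preference and simple heuristics".

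**The concern.** To match a patient to a treatment, one must know whether that patient would do better on one option than on another. A predictor of outcome among people who all received an option does not show this. Participants enter when they are seeking care, so natural recovery and regression to the mean are plausible, and a marker of either would look like a marker of response.

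Two things are at stake. A prognostic marker could be presented as a guide to treatment choice. And the randomised assignments, the one part of the design that can separate prognosis from effect, are not linked to Aim 2. The two apps are also pooled under one label, although they deliver different therapies with different staff support.

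**Working it through.** **1. Inputs.** From the documents: three Phase 1 arms, two apps, 4,500 participants (Screening and Recruitment). Not in the documents, and assumed here: 1:1:1 arms, 1:1 apps, random app assignment, outcome SD 1, two-sided 5% level, 80% power, 50-100% follow-up. The 4,500 cannot be reproduced, because no effect size, SD, power or dropout is given for it.

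**2. What a treated-only model estimates.** Let a marker have prognostic slope *b* and let it modify the effect of treatment by *g* per SD. The slope within the treated arm is *b + g*. In an untreated comparator it is *b*, so the between-arm difference in slopes is *g*. If the comparator is itself active, the difference is *g*(one option) minus *g*(the other), which is a relative quantity.

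A simulation with 1,500 per arm and 400 replicates gave:

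| Marker | Slope in treated arm | Between-arm difference |
|---|---|---|
| Purely prognostic (*b* = -0.30, *g* = 0) | -0.30 | 0.00 |
| Pure effect modifier (*b* = 0, *g* = -0.20) | -0.20 | -0.20 |

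The treated-arm column cannot tell the two kinds of marker apart; the between-arm column can.

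**3. Illustration with no treatment effect.** With equal variances and baseline-to-follow-up correlation *r*, corr(baseline, change) = (*r* - 1)/√(2(1 - *r*)) = -√((1 - *r*)/2). For assumed *r* = 0.5 this is -√0.25 = -0.50; for 0.6, -√0.20 = -0.45; for 0.7, -√0.15 = -0.39. Change is then partly predictable although treatment does nothing.

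**4. What the assignments can identify.**
- App+EF+SF versus EF+SF: who gains from adding an app to enhanced feedback.
- App+EF+SF versus App+SF: who gains from adding enhanced feedback to an app.
- EF+SF versus App+SF: who does better on one than the other.
- Headspace versus SilverCloud, within the app arms: the same question for the two apps, each with its support.

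Every participant has standard feedback and every arm adds something to it, so no contrast shows benefit over standard feedback alone. None of these contrasts compares clinic treatments.

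**5. Precision.** With *n* per arm and a 50/50 predictor, each subgroup effect has variance 2/(*n*/2) = 4/*n*, and their difference has 8/*n*. The detectable difference is (1.960 + 0.842)√(8/*n*). Per SD of a continuous predictor it is 2.802√(2/*n*).

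| Follow-up | *n* per arm | 50/50 predictor | Per SD, continuous | 50/50, Bonferroni for 20 predictors |
|---|---|---|---|---|
| 100% | 1,500 | 0.205 | 0.102 | 0.282 |
| 80% | 1,200 | 0.229 | 0.114 | 0.316 |
| 60% | 900 | 0.264 | 0.132 | 0.364 |
| 50% | 750 | 0.289 | 0.145 | 0.399 |

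The app contrast has the same precision: two app arms give 2*n* people, hence *n* per app. A 0.2 SD subgroup difference needs 8 × (2.802/0.2)² ≈ 1,570 per arm, or 4,710 in all, slightly above the planned 4,500 even with complete follow-up. No credit is taken here for the variance that baseline adjustment would remove.

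**The case against.** The strongest reply is that the protocol does not describe the Aim 2 models. Change scores appear for summaries and for the genetic regressions, not for machine learning, so one cannot say that the models will predict change, or that the randomisation was deliberately set aside. The t-tests may well compare arms for Aim 1. This stands: the documented facts are an undefined response, no comparator and no specified interaction.

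A reader might also infer that Aim 2 would simply find the patients who improve anyway. That goes too far. A treated-only model mixes the two sources, and a true modifier shows up in it as well; it just cannot be recognised as one.

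Nor does the baseline-change correlation measure the error in Aim 2. The predictors Aim 2 names are mobile, genomic and environmental data, and adjusting for baseline removes that artefact. Adjustment does not, however, turn other prognostic markers into evidence of differential benefit.

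It is also fair that the ANALYSIS PLAN puts feasibility and acceptability first, and that no rule for recommending treatment is planned. But the same section wants data that help inform treatment decisions, and the matching goal is stated outright. Limited power for interactions is real; it limits how many predictors to test, not whether the interaction is the right quantity.

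**Conclusion.** The point holds in this form: the stated goal is differential benefit, and nothing specified for Aim 2 can separate it from prognosis. The only predictor-of-change analysis that is written down omits arm. For the mobile interventions the trial already makes the assignments needed for a better analysis, so this is more than missing detail. It should be settled before analysis; it does not undermine the arm comparisons of Aim 1.

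The size is a matter of what can be claimed. Under the stated assumptions, interactions of about 0.21-0.29 SD between two equal subgroups are detectable for a single pre-specified predictor. A search over 20 predictors raises this to about 0.28-0.40 SD, so a wide search would be exploratory.

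The documents do not support two stronger readings: that using the randomised contrasts would show who benefits from mobile tools over standard feedback alone, or that it would rescue matching for drug or psychological treatment. The first lacks an arm and the second lacks randomisation.

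**What to change.** **Aim 2(a).**
- Define response as the follow-up score on one named scale at one named survey, adjusted for baseline.
- Include randomised arm (all three pairwise contrasts) and, within the app arms, assigned app, with their interactions with a few pre-specified baseline predictors.
- Report app effects separately for Headspace and SilverCloud.
- Add the arm interaction to the variant and PHQ-change analysis.
- Base any matching statement on these interactions only, and check any wider machine-learning search out of sample.
- State that the contrasts show incremental or relative benefit among mobile interventions.

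**Analysis set.** The Phase 1 section says that patients waiting less than two weeks are still randomised to the three groups; the App-Based Interventions section says they are outside the initial randomisation. Reconcile these before defining the randomised set, and confirm that computer assignment of the app is random for everyone.

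**Aim 2(b).** Label results as prognostic under the clinic treatment received, with assigned arm and app as covariates because app access continues in Phase 2. The alternative is to pre-specify a confounding-adjusted comparison between treatments, with its assumptions.

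**Cost.** Changes to the analysis and to the wording of the aim; the assignments and baseline measures are already in the protocol. The price is wider intervals, fewer predictors and a more modest claim for clinic treatments.

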## **RESEARCH DESIGN AND METHODS**

This study will have **two phases**, each with different study designs:

**Phase 1** will cover the period while individuals are waiting for care. The design of this phase is a randomized clinical trial, wherein participants are randomly assigned to one of three study conditions that vary by the type of Mobile Health (mHealth) intervention they can receive.

**Phase 2** begins when a participant has a first appointment for outpatient mental health care, and uses a cohort study design for measuring outcomes associated with clinic-based treatments.

### **Phase 1**

Patients with scheduled intake mental health appointments, pre-screening mental health appointments, on the waitlist/referral list, or identified as a potential patient seeking mental health care at Michigan Medicine or University Health Services will be recruited to participate in the study. Patients can be recruited at any time between the appointment being scheduled to up to one month following their intake appointment.

Participants that are enrolled with sufficient time before their scheduled appointment ( $\geq 2$  weeks) will be randomized to one of **three groups**:

- 1) Enhanced Feedback + Standard Feedback (**EF+SF**): Participants will receive enhanced feedback from the MyDataHelps study app in addition to standard feedback from the Apple Watch health app or Fitbit activity tracker
- 2) App-Based Intervention + Standard Feedback (**App+SF**): Participants will receive an app-based intervention in addition to standard feedback from the Apple Watch health app or Fitbit activity tracker
- 3) App-Based Intervention + Enhanced Feedback + Standard Feedback (**App+EF+SF**): Participants will receive an app-based intervention, enhanced feedback from the MyDataHelps study app, and standard feedback from the Apple Watch health app or Fitbit activity tracker

Some patients may have a shorter waiting period (<2 weeks) prior to their intake appointment (e.g., due to acute mental health symptoms). These patients will also be contacted for recruitment to provide opportunity for benefit from the research and from access to the mHealth interventions and will still be randomized to one of the above-listed groups.

As part of the enrollment process, participants will be guided by a study team member through **three processes**:

1. **Download Study App:** Participants will download the study app, MyDataHelps, on their smartphone. MyDataHelps is a commercially available application developed by CareEvolution. This app serves as a vehicle for consent, data collection, delivery of all study questionnaires, automated notifications, and reminders. The app will also receive data from the Health app and study devices. Participants will be asked to complete daily mental health symptom assessments via the app throughout the duration of their enrollment in the study. The app will also present enhanced feedback on participant progress via a personalized “dashboard.” If participants are utilizing an Apple Watch with their existing iPhone, they must enable MyDataHelps to read out the data fields in the Health app. This will be made clear to

participants during the consent process, so a participant can decide if they are still interested in participating.

2. **Receive Device:** Participants will be provided with an Apple Watch or Fitbit to sync with their smartphone. Participants with iPhones will be provided with Apple Watches or Fitbits and participants with Androids will be provided with Fitbits, or similar smart watches and activity trackers for both types of phones. This device will be worn throughout their entire involvement in the study. This will allow for collection of objective data on daily activity, such as steps/physical activity, sleep, and heart rate.
3. **Download App-Based Intervention:** Participants randomized to the groups receiving app-based interventions will download additional apps to their smartphones that are designed to address mental health symptoms. Participants will be computer-assigned to one of the two app-based interventions (mindfulness via the Headspace app or cognitive behavioral therapy via the SilverCloud app). A study team member will guide them through the process of downloading the app to their phone at that time.

Participants will also be asked for permission for the study team to collect active (e.g., symptom self-reports) and passive (e.g., screen time) data through their smartphone through the duration of the study.

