## **Screening and Recruitment**

Participant screening and recruitment will be managed by study staff. All study team members are required to complete team/study training and all appropriate regulatory training and disclosures.

The study will recruit 4,500 participants via patients at Michigan Medicine and student patients at University Health Service (UHS). Potential study participants will include adult patients (age 18+) that are scheduled for an intake mental health appointment, pre-screening mental health appointment, on the waitlist/referral list, or identified as a potential patient seeking mental health at either Michigan Medicine or UHS. These appointments are generally scheduled with a 3-10 week waiting period. Patients will be invited to participate in the study as soon as possible after scheduling their appointment in order to best maximize participation during their full waiting period.

A waiver of HIPAA authorization is requested in order for study staff to:

- 1) Receive daily lists of patients for whom a mental health intake appointment has been scheduled at each recruitment site
- 2) Access the Michigan Medicine and UHS electronic health records to confirm eligibility of listed patients and obtain contact information

Study staff will employ the following **recruitment strategies** to contact, screen, and enroll potential participants:

1. At the time of scheduling their intake mental health appointment, patients may be informed by call center staff that they may be contacted about a new study.

2. Daily lists of newly scheduled appointments and individuals on the waitlist/referral list will be generated by the Michigan Medicine Department of Psychiatry call center, UHS scheduling, or from the Research Data Warehouse (RDW) and provided to study staff.
3. Using existing Research Data Warehouse information, a patient is prospectively identified as someone who meets the study criteria during the screening process. Potentially eligible patients may be contacted by email/text message/phone call to introduce the study, with an invitation to contact the study team by phone or email if interested in participating.
4. Prior to contacting patients by phone/text message/phone call, study staff will complete preliminary screenings via listed patients' electronic health records to determine whether basic, objective inclusion criteria are met (e.g., scheduled outpatient mental health appointment, age 18+).

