### **Enrollment**

Participants will complete several steps prior to enrollment being considered as “completed.”

Participants must complete the following steps to be enrolled in the study:

1. MyDataHelps study app download, installation, and account creation
2. Completion of informed consent
3. Completion of baseline survey via the MyDataHelps study app
4. Download and installation of assigned app-based intervention (Headspace or SilverCloud), if applicable
5. Receipt of device (Apple Watch or Fitbit) and agreement to wear the device regularly. Participants’ devices will be mailed, unless they indicated that they would like to meet with study staff to receive their device in person.
6. Pairing and setup of smartphone, device (Apple Watch or Fitbit), and MyDataHelps study app

Study staff are available by phone or email as necessary to provide technical support to aid participants in downloading apps, completing informed consent, or setting up their devices. Participants may also opt to meet with study staff in person, as described above.

Participants will be offered to complete consenting and enrollment steps remotely (via telephone with a study team member and on their own following their download of the MyDataHelps study app). If further assistance is needed, participants may opt to meet recruitment staff in person for support with downloading app(s), completing the informed consent process, completing the baseline survey, or picking up and configuring their Apple Watch or Fitbit. Patients who begin the recruitment process online may also opt to meet recruitment staff in person to complete the remainder of the process (e.g., informed consent, enrollment, downloading apps). In-person meetings may take place in a designated study space at Michigan Medicine or UHS or at an agreed-upon location in the community (e.g., coffee shop, campus library).

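### The protocol gives two incompatible allocation rules for patients with less than two weeks' wait, and no Aim 1 analysis set says how patients assigned only between the two apps would be analysed

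*Combined protocol and SAP*

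**What the plan says.** The combined protocol and SAP describes Phase 1 under Research Design and Methods as a randomised trial in which "participants are randomly assigned to one of three study conditions", with no exception for short waits.

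The Phase 1 section first describes three-group randomisation for "Participants that are enrolled with sufficient time before their scheduled appointment", meaning at least two weeks. It then says that patients with a shorter wait "will still be randomized to one of the above-listed groups": EF+SF, App+SF or App+EF+SF. It gives acute symptoms as an example of why a wait may be short.

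The App-Based Interventions section says of those recruited less than two weeks before their appointment: "and thus not included in the initial randomization) will receive access to one of the two apps at the time of their intake appointment". Which of the two apps each patient gets is "also based on computer random assignment". That section does not say whether they receive enhanced feedback.

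Other relevant text:
- Screening and Recruitment: "These appointments are generally scheduled with a 3-10 week waiting period". Short-wait patients may be screened, consented and enrolled at the intake visit itself.
- Phase 1: "Patients can be recruited at any time between the appointment being scheduled to up to one month following their intake appointment".
- Enrollment: one of the steps that completes enrolment is "Download and installation of assigned app-based intervention (Headspace or SilverCloud), if applicable".
- Surveys: University Health Service (UHS) waits tend to be shorter.
- Analysis Plan: t-tests and chi-square tests, with no analysis set, no named contrast and no adjustment for wait or site.

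**The concern.** Who can be allocated to which arm is a basic element of a randomised trial. Here two current statements answer that question differently for the same patients, and staff at two recruitment sites could each follow a different one.

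Under the App-Based Interventions rule, a short-wait patient has no chance of being in EF+SF. If such patients were counted in the app arms, those arms would contain a type of patient that EF+SF lacks. The protocol itself links short waits to acute symptoms and to site, and either could be prognostic. Aim 1 claims effectiveness of the app and feedback interventions, so the app-versus-EF+SF contrast is the one at risk. The direction of any bias cannot be predicted.

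**Working it through.** **Step 1: can the two rules be reconciled?**

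| Question | Phase 1 section | App-Based Interventions section |
|---|---|---|
| In the three-group randomisation? | Yes | Not in the initial one |
| Can the patient be in EF+SF (no app)? | Yes | No, all receive an app |
| What is random? | Group | Headspace or SilverCloud only |
| Enhanced feedback? | Fixed by group | Not stated |
| Two-week line tied to | Being enrolled | Being recruited |

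Reading the word initial as randomised later does not help, because the second rule still gives every short-wait patient an app. The Research Design and Methods section agrees with the Phase 1 section, but nothing withdraws the other rule. The last row is a smaller drafting point: enrolment is complete only after the assigned app is installed, so a line drawn at completed enrolment would fall after assignment.

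**Step 2: size, for illustration only.** The plan has no figure to reproduce. From the documents: N = 4,500 (recruitment target). Assumed: all analysed; 1:1:1 for the remaining patients; short-wait share f of 5% or 10%; the app-only rule is followed and these patients are split evenly over the two app arms; gap g of 0.1 to 0.3 SD between short-wait and other patients on the outcome compared; no true effect; two-sided 5% test.

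- EF+SF size: n_EF = 4500(1 − f)/3
- Each app arm: n_app = n_EF + 4500f/2
- Short-wait fraction of an app arm: p = (4500f/2)/n_app
- Bias = p × g; SE = √(1/n_app + 1/n_EF)
- Rejection rate = P(|Z + bias/SE| > 1.96)

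| f | n_EF | n_app | p | Bias (SD), g = 0.1 to 0.3 | SE | Rejection rate |
|---|---|---|---|---|---|---|
| 5% | 1,425 | 1,537.5 | 7.3% | 0.007 to 0.022 | 0.0368 | 5.5% to 9% |
| 10% | 1,350 | 1,575 | 14.3% | 0.014 to 0.043 | 0.0371 | 7% to 21% |

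If only 60% were analysed (2,700, assumed), the bias is the same and the rates are 5.3% to 7.5% and 6% to 15%.

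**Step 3: dependence on the even split.** Since enhanced-feedback status is unstated, the split is a guess. With an even split, App+EF+SF versus App+SF is unbiased. If all short-wait patients went to App+SF, that arm would have 1,425 + 225 = 1,650 or 1,350 + 450 = 1,800 patients, with short-wait fractions of 13.6% or 25.0%. Its contrast with EF+SF would then have a bias of 0.014 to 0.041 SD or 0.025 to 0.075 SD. App+EF+SF versus EF+SF would have none, and App+EF+SF versus App+SF would be shifted by the same amounts as App+SF versus EF+SF.

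**Step 4: cost of leaving these patients out.** Detectable difference at 80% power, two-sided 5%, all analysed = 2.80 × √(2/n per arm): 0.102 SD at n = 1,500, 0.105 SD at 1,425 and 0.108 SD at 1,350.

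**The case against.** The strongest reply is that harm needs four things together: the app-only rule governs, its patients are counted in the app arms, their share is material, and they differ in outcome. No text plans the second, and calling these patients outside the initial randomisation leans against it. The share and the gap are undocumented, and waits of generally 3 to 10 weeks point to a low share. The Analysis Plan also puts feasibility and acceptability first and names no alpha or primary contrast. All of this stands. It limits the size of the problem, but it does not remove the contradiction.

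A reader might infer more than the documents support:
- **That the Aim 1 comparison is biased as planned.** It is not, if the Phase 1 rule is followed or if app-only patients are left out.
- **That the false-positive rate could be very high.** That needs short-wait shares well above 10%. Late recruitment or short UHS waits might raise the share, but no document gives such a figure.
- **That people without an appointment date have no allocation rule.** The general three-condition statement covers them on its face. Patients recruited after intake are less clear, because Phase 2 begins at the first appointment.
- **That patients randomised at or after intake should be dropped to remove bias.** If randomised among the three groups they do not unbalance the arms. Dropping them changes the population studied, and would lose properly randomised patients enrolled at the intake visit.

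**Conclusion.** The allocation rule for short-wait patients is wrong as written: two current statements conflict and nothing in the document settles which applies. That conclusion rests on the text alone and is firm.

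The statistical consequence is conditional. Bias arises only if the app-only rule is followed and its patients are pooled into the app arms; otherwise none is expected. Under the stated assumptions it is a few hundredths of an SD or less for an even split at shares of 5% to 10%, and up to 0.075 SD if all these patients entered one arm at a 10% share. The share, the gap and the split are assumptions, so these figures, and the rejection rates with them, give only a scale. The absence of an analysis set is a general gap in the Analysis Plan; this is one place where it matters.

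**What to change.** 1. Reconcile the Phase 1 and App-Based Interventions sections into one allocation rule. If a two-week line is kept, measure it at one date fixed before assignment. Confirm which rule applies to patients recruited after intake. The choice of rule is the sponsor's.
2. Define the Aim 1 between-arm analysis set as all participants randomised among all three groups, analysed as assigned, including those randomised at the intake visit.
3. Report any patients assigned only between the two apps separately and outside the Aim 1 contrasts.
4. Optional: a sensitivity analysis limited to patients randomised before intake, to match Aim 1's waitlist population. Label it as a change of population and not as a bias correction.

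The cost is protocol wording and one analysis-set definition; the survey schedule does not change. If short-wait patients prove to have been assigned only between apps and are therefore excluded, the detectable difference rises from 0.102 SD to 0.105 SD at a 5% share or 0.108 SD at 10%. If they are randomised among the three groups, they stay in and nothing is lost.
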